9.1.3 Tissue banking

All leftover tissue will be banked in either the Center for Immuno Oncology, lab of [name] PhD or the lab of [name] PhD as per standard lab protocol, such that it can be used for additional or optional future analyses as needed.

These analyses may include RNA analyses using the most current and informative methodologies at the time that correlative science is performed on all specimens. NanoString signatures and comprehensive RNA sequencing may be used.

Additionally, available tissue, may be used for whole exome sequencing to determine mutational burden and neoantigen detection, T-cell receptor sequencing to determine intratumoral TCR diversity and flow cytometry to quantify immune populations.

9.2 Characterizing immune markers in serum and peripheral blood mononuclear cells (PBMCs) prior to and after therapy with pembrolizumab plus radiotherapy

9.2.1 Hypotheses

- We hypothesize that the immune marker profile in the peripheral blood will change over the course of pembrolizumab plus radiation.
- We hypothesize that a larger increase in markers of immune activity in the peripheral blood will correlate with a better disease response as assessed on concurrent restaging scans, and in terms of best radiographic response at any time on trial.
- We hypothesize that an immune marker or composite of markers in the peripheral blood at baseline will correspond to TIL percentage in baseline tumor biopsy

9.2.2 Collection, handling, and shipping of blood specimens

Research blood collection is performed for cytokine analyses, CyTOF, flow cytometry and potential DNA isolation. The samples will be banked in the DFCI Center for ImmunoOncology laboratorites and/or laboratory of [name] MD PhD and/or the lab of [name] PhD for these and future research purposes. These specimens will become the property of the DF/HCC.

Blood draws should not be performed on Friday afternoons, as there may not be time for processing of the blood. If a blood draw must be performed on Friday morning, the lab of [name] must be notified ahead of time to ensure that there will be adequate time for processing the blood, since it cannot be stored over the weekend. PBMC processing can occur as below at the DFCI or may be performed locally and then PBMC subsequently shipped for future analyses.

CONFIDENTIAL

This document is confidential. Do not disclose or use except as authorized.

The following research blood samples are obtained at the correlative timepoints:

- Five 10 mL green-top (heparin) tubes for PBMC analyses

All samples should be de-identified and labeled with the Participant initials, Participant Study ID number and date of collection and time point (e.g., “Baseline” or “Cycle 2” or “Cycle 3”).

All samples will then be hand carried at ambient temperature or immediately mailed to [name] at:

Center for Immuno-Oncology
Dana-Farber Cancer Institute
[name]
[name]
[contact]
Pager: [name]

Blood must be processed within 3-4 hours of its being drawn.

9.2.3 Assays on serum and isolated PBMCs

Studies of immune function performed on blood will include:

- Analysis of antibody response (both quantitative antibody titer and qualitative antibody binding and functionality)
- Study of T-cell composition and functioning
- Analysis of cytokine response
- Identification of circulating antigen
- Comparison of immune responsiveness in serum
- Analysis of blood cell composition using flow cytometry
- Effect of immune status on circulating tumor cells
- Analysis of genomic or protein polymorphisms that may affect immune functioning and inflammation
- Analysis of inflammatory status in correlation to toxicity response
- Analysis of intracellular signaling pathways

9.3 Correlative studies to be performed on staging PET-CT and/or CT chest, abdomen and pelvis, and/or staging MRI scans

9.3.1 Hypotheses

The likelihood of abscopal responses following radiotherapy in the setting of immunotherapy may depend on the likelihood that activated T-cells will traffic from the irradiated site or relevant draining lymph nodes to other, unirradiated tumor deposits. We will test this hypothesis by correlating an algorithm incorporating tumor location and size to predict T-cell trafficking with abscopal responses seen in the context of this trial. We will also test our ability to predict which particular distant metastatic lesions will respond following targeted radiation therapy.

9.3.2 Collection of imaging data

CONFIDENTIAL

This document is confidential. Do not disclose or use except as authorized.

Imaging studies will be performed according to the study schedule. No investigational imaging modalities will be performed as part of this study. Initial staging studies will be deidentified and saved as DICOM data on a password protected server for analyses by study personnel.

9.3.3 Analysis of imaging data

Identification of potential target lesions will be performed by treating physicians, study investigators, and the TIMC, as appropriate. Prioritization of lesions will occur as previously described. We will then rank the lesions according to an algorithm previously described that may predict the likelihood of generating an abscopal response [61]. We will correlate the rankings with abscopal responses, as well as attempt to predict which distant lesions respond. We will also explore whether hypothesis guided targeting of irradiated lesions is feasible and consistent with palliative radiation therapy by calculating the likelihood that a top ranked lesion would be a safe and feasible target for treatment.

CONFIDENTIAL

This document is confidential. Do not disclose or use except as authorized.

9.4 Additional analysis

The above-mentioned analyses may be altered based on novel developments in the field of cancer immune profiling at the time of correlative science. Additional markers or alternative technologies (based on scientific developments and/or novel technologies) may also be used, to explore potential prognostic or predictive candidate markers/panels or markers related to treatment benefit and/or safety, to improve diagnostic tests, or to understand SCCHN cancer biology.

9.5 Site Performing Correlative Studies

Pathological studies will be conducted by the Center for Immune Oncology at the DFCI. QualTek, Nanostring, and other external fee-for-service services may also be performed on deidentified specimens and used for PD-L1, RNA and other analyses as specified above. Flow cytometry assessment of both tissue and blood will be performed by the Center for Immune Oncology at the DFCI. Other analyses on tumor tissue and collected samples will be performed in the laboratory of [name], a surgical oncologist at the Dana Farber Cancer Institute, who has performed similar analyses on other human tissues. Deidentified data related to correlative analyses will be shared with NYU Langone Health as a collaborator to assist with data analysis and manuscript writeup, with an agreement in place prior to sending any deidentified data.

10. STUDY CALENDAR

Baseline evaluations are to be conducted within **28 days** prior to start of protocol therapy (except for pregnancy test and baseline tumor biopsy, as detailed). If these screening assessments occur within 3 days before start of study treatment, then they may serve as the baseline Cycle 1 Day 1 values. Scans must be done within **28 days** prior to the start of therapy. Radiation simulation scan can provide more recent tumor measurements prior to the start of study treatment when available.

As detailed in the Study Calendar, a negative pregnancy test in women of child-bearing potential must be documented within **7 days** before the first dose of study medication.

A baseline tumor biopsy, obtained within **28 days** before starting protocol therapy, is also encouraged if tumor tissue is safely accessible. A second optional tumor biopsy sample will be obtained at the end of cycle 2, within 21 days of cycle 3, day 1.

In the event that the participant's condition is deteriorating, laboratory evaluations should be repeated within 48 hours prior to initiation of the next cycle of therapy.

Assessments must be performed prior to administration of any study agent. Study assessments and agents should be administered within \pm 3 days of the protocol-specified date, unless otherwise noted.

CONFIDENTIAL

This document is confidential. Do not disclose or use except as authorized.

Table 8: Study Calendar

	Screening ^a	C1 D1	C1 D1-D21	C2 D1	C2 D14-D20	Cycle 3 and subsequent cycles	Off-Study ^l	Follow- Up
						D1		
Pembrolizumab ^b		X		X		X		
Radiotherapy ^b			X					
Informed consent	X							
Demographics	X							
Medical history	X							
Concurrent medications ^c	X	X-----X						
Physical exam	X	X		X		X	X	
Vital signs	X	X		X		X	X	
Weight	X	X		X		X	X	
Performance status	X	X		X		X	X	
Hematology panel (CBC with platelets)	X	X		X		X	X	
Chemistry panel ^d	X	X		X		X	X	
Coagulation panel (PT/PTT)	X							
Pregnancy test ^e	X							
EKG	X							
Tumor archival (optional)	X ^f							
Tumor biopsy (suggested)	X ^g				X ^h			
Adverse event evaluation	x	X-----X						
Tumor measurements	X	Tumor measurements are repeated at week 5(+/- week) and then every 8 weeks (+/- week). Documentation (radiologic) must be provided for participants removed from study for progressive disease. Confirmatory scans 4 weeks after documented response will be obtained						X ⁱ
Blood collection for correlative science ^j	X			X		X		
TSH ^k	X					X		
MD/NP/PA evaluation required		X		X		X	X	
Survival								X ^m
HIV Test ⁿ	X							

CONFIDENTIAL

This document is confidential. Do not disclose or use except as authorized.

^a Baseline evaluations are to be conducted within 28 days prior to start of protocol therapy. If these screening assessments occur within 3 days before start of study treatment, then they may serve as the baseline Cycle 1 Day 1 values. Baseline Laboratory tests must be completed within 14 days prior to first dose of the study drug.

^b As described in section 5, pembrolizumab may start up to 3 days before and 10 days after radiotherapy start, although it is encouraged that pembrolizumab be started after at least several fractions of radiation have been administered. Radiation will be delivered as specified as per Cohort A (5-8 Gy in each of 3-5 fractions) or Cohort B (8 Gy in each of 3-5 fractions to 1-3 lesion, and 20 Gy in 5 fractions to 1-3 additional lesions). As specified in the protocol, radiotherapy during subsequent cycles is acceptable with permission of the PI.

^c See Section 5 for concomitant medications guidelines

^d Chloride, potassium, sodium, BUN, serum creatinine, phosphorus, calcium, albumin, total protein, alkaline phosphatase, ALT, AST, total bilirubin (NOTE: the frequency of checking magnesium levels is left up to the treating provider)

^e In female subjects with child-bearing potential, urine pregnancy test must be performed within **7 days** before the first dose of study medication. If the urine test is positive or cannot be confirmed as negative, then a serum test is required to confirm the subject is not pregnant.

^f Archival tumor samples should be collected (block or if not possible, 20 unstained slides) – both the most recent biopsy as well as prior to the start of any PD-1 directed therapy.

^g Baseline tumor biopsy obtained within 28 days before starting protocol therapy is suggested for those with accessible tumor tissue. See Section 9.1.2 for biopsy handling and processing instructions.

^h A second optional tumor biopsy will be performed in patients at the end of cycle 2, prior to cycle 3 day 1 of protocol therapy (ideally as close to administration of cycle 3 day 1 therapy as possible).

ⁱ For those taken off the study for toxicity tumor measurements should be repeated every 6 weeks. Patients with documented PD will be removed from the treatment and followed for overall survival every 6 months, until death (by phone).

^j See Section 9 for blood handling and processing instructions.

^k TSH is only required every 3 cycles

^l Off-Study visit is to occur within 30 days of final administration of study treatment (week 52 at the latest). End of treatment assessments do not have to be repeated if the same assessments were performed within 7 days prior to the visit.

^m Patients with documented PD will be followed for overall survival every 6 months or until death.

ⁿ A negative HIV test must be recorded prior to treatment

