5.3.2 End-of-Treatment Procedures

End-of-Treatment Visit

All subjects will be asked to return to the site for a final, End-of-Treatment visit, if possible. This visit must be performed within 30 days of final administration of study treatment. End-of-treatment assessments will not have to be repeated if the same assessments were performed within 7 days of this visit.

Record:

- For patients who come off for reasons other than progressive disease: Tumor assessments to be performed every 6 weeks if patients come off within one year of therapy. If study treatment is discontinued due to PD, then tumor assessments are not required for that subject.
- ECOG PS
- Physical exam
- Vital signs and weight
- Concomitant medication use
- AEs or SAEs

Draw blood sample for:

- Hematology (Table 2)
- Chemistry panel (Table 2)

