5.8 Criteria for Taking a Participant Off Protocol Therapy

Duration of therapy will depend on individual response, evidence of disease progression and tolerance. In the absence of treatment delays due to adverse event(s), treatment may continue until one of the following criteria applies:

- Disease progression. In the case of progressive disease, confirmatory scans are recommended between 4-8 weeks following the date of initial progression along with continued treatment, provided the patient is thought to be deriving clinical benefit and is counseled regarding the risks and benefits of continued treatment. If progression is confirmed, date of progression is dated at the time of the original scans. If progression is confirmed, continued treatment is only allowed if irRC demonstrates a response or stable disease, again provided the patient is thought to be clinically benefitting and is counseled regarding the risk and benefits of remaining on treatment.
- Intercurrent illness that prevents further administration of treatment
- Unacceptable adverse event(s)
- Participant demonstrates an inability or unwillingness to comply with the oral medication regimen and/or documentation requirements
- Participant decides to withdraw from the protocol therapy
- General or specific changes in the participant's condition render the participant unacceptable for further treatment in the judgment of the treating investigator

Participants will be removed from the protocol therapy when any of these criteria apply. The reason for removal from protocol therapy, and the date the participant was removed, must be documented in the case report form (CRF). Alternative care options will be discussed with the participant.

A Treatment Ended/Off Study Form will be filled out within OnCore, when a participant is removed from protocol therapy.

In the event of unusual or life-threatening complications, treating investigators must immediately notify the Overall PI, [name] at [name] (pager #).

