11.1.4 Response Criteria

11.1.4.1 Evaluation of Target Lesions (Note: irradiated target lesions are excluded from overall response determination)

Complete Response (CR): Disappearance of all target lesions. Any pathological lymph nodes (whether target or non-target) must have reduction in short axis to <10 mm.

Partial Response (PR): At least a 30% decrease in the sum of the diameters of target lesions, taking as reference the baseline sum diameters.

Progressive Disease (PD): At least a 20% increase in the sum of the diameters of target lesions, taking as reference the smallest sum on study (this includes the baseline sum if that is the smallest on study). In addition to the relative increase of 20%, the sum must also demonstrate an absolute increase of at least 5 mm. (Note: the appearance of one or more new lesions is also considered progressions).

Stable Disease (SD): Neither sufficient shrinkage to qualify for PR nor sufficient increase to qualify for PD, taking as reference the smallest sum diameters while on study.

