11.2.2 Impact of New Lesions on irRC

New lesions in and of themselves do not qualify as progressive disease. However, their contribution to total tumor burden is included in the SPD which in turn feeds into the irRC criteria for tumor response. Therefore, new non-measurable lesions will not discontinue any subject from the study.

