11.2.6 Immune-Related Best Overall Response Using irRC (irBOR)

irBOR is the best confirmed overall response over the study as a whole, recorded between the date of first dose until the last tumor assessment before subsequent therapy (except for local palliative radiotherapy for painful bone lesions) for the individual subject in the study. For the assessment of irBOR, all available assessments per subject are considered.

irCR or irPR determinations included in the irBOR assessment must be confirmed by a second (confirmatory) evaluation meeting the criteria for response and performed no less than 4 weeks after the criteria for response are first met.

11.2.7 Local response is defined as irRC applied to the irradiated lesions. This is not applicable in the case of an irradiated bone lesion.

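### Table 8 and 1.1 stop pembrolizumab at progression without exception, but 5.8 allows conditional treatment past it, so exposure and the scans behind irRC and local response can depend on which section a site follows

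*Combined protocol and SAP*

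**What the plan says.** **Stopping without exception.** Section 10, Table 8, footnote i: "Patients with documented PD will be removed from the treatment and followed for overall survival every 6 months, until death (by phone". The design summary in 1.1 also gives pembrolizumab every 21 days up to progression, for both cohorts, with no exception.

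**Stopping with exceptions.** Section 5.8 lists progression as a reason to end therapy and then qualifies it: "In the case of progressive disease, confirmatory scans are recommended between 4-8 weeks following the date of initial progression along with continued treatment". The condition is that the patient is thought to be benefiting and is counselled. After confirmation, "If progression is confirmed, continued treatment is only allowed if irRC demonstrates a response or stable disease", again subject to perceived benefit and counselling. The same section closes by saying that participants come off therapy when any listed criterion applies.

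**New lesions.** Section 11.1.4 (RECIST 1.1) states that "the appearance of one or more new lesions is also considered progressions". Section 11.2.2, within the irRC definitions, says: "Therefore, new non-measurable lesions will not discontinue any subject from the study". Section 5.10 lists the off-study reasons as loss to follow-up, withdrawal of consent for data submission, and death. Progression is not among them.

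**Scans.** On treatment, scans fall at week 5 (give or take a week) and then every 8 weeks (5.3.1). After stopping, 5.3.2 says: "If study treatment is discontinued due to PD, then tumor assessments are not required for that subject". For best irRC response, 11.2.6 says "For the assessment of irBOR, all available assessments per subject are considered", up to the last assessment before subsequent therapy, and it requires confirmation of a response at least 4 weeks later. Local response (11.2.7) is irRC applied to the irradiated lesions. Both are secondary endpoints, reported with 90% exact intervals (13.5).

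**The concern.** A patient with RECIST progression who is thought to be benefiting comes off treatment under Table 8 and 1.1, but may stay on under 5.8. Because scans are not required after stopping for progression, the choice of section affects both how much pembrolizumab the patient receives and whether any later scan exists.

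The irRC response rate is meant to pick up response after RECIST progression, and section 2.1.1.3 itself notes that such responses have been seen. If sites follow different sections, that rate partly reflects which section each one read. The protocol provides for external sites (Appendix J), so divergent practice is plausible.

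Local response is exposed by a second route. Section 11.1.4.1 excludes irradiated target lesions from the overall response determination. Progression by target-lesion growth therefore comes from disease outside the irradiated field, yet it removes the requirement to go on imaging the irradiated lesion.

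**Working it through.** **1. The plan's own figures.** The rates used below come from 13.1, so the design was checked first. With 6 patients at stage 1, 13 more if at least 2 are progression-free, and success at 10 or more of 19:

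P(success) = sum over x = 2 to 6 of P(X1 = x) × P(X2 ≥ 10 − x), with X1 ~ Bin(6, p) and X2 ~ Bin(13, p).

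- p = 0.65: 0.9018 (stated power 90%).
- p = 0.35: 0.0842 (stated level 0.08; agrees to two decimals).

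The design figures reproduce, and this point does not dispute them.

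**2. The instructions side by side.**

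| Situation | Table 8 note i and 1.1 | 5.8 | 11.2.2 |
|---|---|---|---|
| First RECIST PD, not thought to benefit | stop | stop | silent* |
| First RECIST PD, thought to benefit, counselled | stop | may continue to a scan at 4–8 weeks | silent* |
| Confirmed PD, irRC response or stable disease, benefiting, counselled | stop | may continue | silent* |
| Confirmed PD, irRC progression | stop | stop | silent* |

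*Unless PD rests on new non-measurable lesions. In that case 11.2.2 says the subject is not discontinued from the study.

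The conflict lies in the second and third rows. Reading the footnote's documented progression as confirmed progression would settle the second row but not the third, because 5.8 allows treatment past confirmed progression too.

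**3. Effect on scans.** A confirmed irRC response needs two assessments at least 4 weeks apart. A patient stopped for PD at week 5 with no later scan has one post-baseline assessment, so no confirmed irRC response is possible. Under 5.8 a second scan would fall between weeks 5 + 4 = 9 and 5 + 8 = 13. Section 11.2.7 does not say whether the confirmation rule applies to local response.

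**4. Effect on exposure.** Assume infusions on days 1, 22, 43, 64 and 85 (nominal 21-day schedule, visit windows ignored). Infusions between the PD scan and the confirmatory scan:

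| PD scan | Confirmed at +4 weeks | Confirmed at +8 weeks |
|---|---|---|
| Week 4 (day 28) | 1 (day 43) | 2 (days 43, 64) |
| Week 5 (day 35) | 1 (day 43) | 3 (days 43, 64, 85) |
| Week 6 (day 42) | 2 (days 43, 64) | 3 (days 43, 64, 85) |

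That is 1 to 3 further infusions under 5.8 and none under Table 8.

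**5. Reach.** Expected number progressed or dead by 3 months = 19 × (1 − PFS rate):

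- PFS 65%: 19 × 0.35 = 6.65, about 7.
- PFS 35%: 19 × 0.65 = 12.35, about 12.

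These are upper bounds on those reaching the conflict by 3 months. They include deaths without PD, and they include patients not thought to benefit, for whom both instructions agree.

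**6. Sensitivity of a response rate.** One patient in 19 is 1/19 = 5.3 percentage points. For illustration, with 90% exact intervals: 2/19 = 10.5% (1.9% to 29.6%) and 3/19 = 15.8% (4.4% to 35.9%). The documents give no rate of response after progression in this population, so the actual shift cannot be calculated.

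**The case against.** The strongest reply is that 5.8 is the dedicated section on ending therapy and so governs. Footnote i hangs on the follow-up cell of the tumor-measurement row, and 1.1 is a summary. On that reading only a cross-reference is missing. This is a reasonable guess at intent, but the documents give no order of precedence, and footnote i states removal from treatment outright.

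Several limits do stand, and they rule out readings that a reader might infer:

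- *Three competing instructions at every first RECIST progression.* Section 11.2.2 covers only new non-measurable lesions and speaks of leaving the study, which 5.10 separates from leaving treatment. Taken literally, it need not collide with footnote i. The wording remains unclear because the tumor-measurement row of Table 8 speaks of removal from study for progression. For other forms of PD there are two positions.
- *Imaging ends at PD, so a site following Table 8 can never record a later irRC response.* Scans are not required, but they are not forbidden. Best irRC response uses whatever exists before subsequent therapy, and 5.9 already obtains outside scans for patients treated away from a study center.
- *The week-5 scan comes too soon after radiation because of the stopping rule.* That interval follows from the scan schedule and is the same under either rule. The stopping rule affects only whether a later scan follows.

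It is also fair to say that 5.8 leaves continuation to judgement, so some variation between sites would remain after the passages are reconciled.

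**Conclusion.** The conflict between Table 8 footnote i and 1.1 on one side and 5.8 on the other is real, and reading documented as confirmed does not remove it. Section 11.2.2 adds to it only for PD resting on new non-measurable lesions. Among PD patients thought to be benefiting, exposure and the availability of scans for irRC and local response can depend on the section applied.

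The number affected is unknown. It is bounded by about 7 to 12 of 19 by 3 months on the design's own rates. Assuming exponential PFS and 3 months = 13 weeks, a reader might go further and take 1 − 0.65^(5/13) = 15% to 1 − 0.35^(5/13) = 33% as the share left with a single scan. That is not supported: the figure pools deaths, some of them before any scan, and includes patients for whom both instructions agree.

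Nor do the documents support a material effect on the primary 3-month PFS rate, because 5.8 dates confirmed progression to the original scan. A small gap remains, since 5.8 does not say how unconfirmed progression is dated. The consequence is therefore confined mainly to descriptive secondary endpoints and to exposure, and its size in response-rate terms cannot be computed. No view is taken on which stopping rule is right.

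**What to change.** 1. Reconcile Table 8 footnote i, 1.1, 5.8 and 11.2.2 into one rule that names the criteria, RECIST 1.1 or irRC, governing removal from treatment. The choice is the sponsor's. State in 11.2.2 whether leaving treatment or leaving the study is meant, consistently with 5.10.
2. Extend the scan retrieval in 5.9 to routine-care scans done before subsequent therapy in patients removed for PD. Read them for irRC and for the irradiated lesions.
3. Report irRC and local response together with the number of patients who have only one post-baseline scan.

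The cost is a wording amendment, a modest extension of scan retrieval and reading, and one extra line in each response table. No added imaging is needed, and the design and sample size are unchanged.
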